^a Adjusted for baseline SER. ^b Adjusted for baseline SER, minimisation variables (i.e. site and ethnicity), age and history of parental myopia (at least one parent). ^c Mean(SD) was calculated with data from both eyes. Mean difference estimate and p value from GEE. ^d Mean difference estimate and p value from ANCOVA. ^e Frequency (%) presented for categorical variables and risk difference and p value from the chi-square test (or fishers exact test if applicable). ^f Mean(SD) and p value from independent samples t-test, no adjustment as tolerability not measured at baseline.

Table XXX: Safety Outcomes by treatment group

	ı	Number of Events	S	Number of Patients						
	Total N=	Atropine sulfate N=	Placebo N=	Total N=	Atropine sulfate N=	Placebo N=	Risk Ratio (95% CI)	p-value		
Adverse Events	n (%)	n (%)	n (%)	n (%)	n (%)	n (%)	xx.x (x.x to x.x)	X.XX		
Adverse Reactions	n (%)	n (%)	n (%)	n (%)	n (%)	n (%)	xx.x (x.x to x.x)	X.XX		
Unexpected Adverse Reactions	n (%)	n (%)	n (%)	n (%)	n (%)	n (%)	xx.x (x.x to x.x)	x.xx		
Serious Adverse Events	n (%)	n (%)	n (%)	n (%)	n (%)	n (%)	xx.x (x.x to x.x)	x.xx		
Serious Adverse Reactions	n (%)	n (%)	n (%)	n (%)	n (%)	n (%)	xx.x (x.x to x.x)	x.xx		
Suspected Unexpected Serious Adverse Reactions	n (%)	n (%)	n (%)	n (%)	n (%)	n (%)	xx.x (x.x to x.x)	x.xx		
Fatal Serious Adverse Events	n (%)	n (%)	n (%)	n (%)	n (%)	n (%)	xx.x (x.x to x.x)	x.xx		

Table XXX: Safety outcomes by system organ class and treatment group

		Nu	ımber of Eve	nts	Number of Patients				
		Total	Atropine sulfate	Placebo	Total N=	Atropine sulfate N=	Placebo N=	RR (95%CI)	p-value
	Blood and lymphatic system disorders	n (%)	n (%)	n (%)	n (%)	n (%)	n (%)	xx.x (x.x to x.x)	x.xx
	Cardiac disorders	n (%)	n (%)	n (%)	n (%)	n (%)	n (%)	xx.x (x.x to x.x)	X.XX
	Gastrointestinal disorders	n (%)	n (%)	n (%)	n (%)	n (%)	n (%)	xx.x (x.x to x.x)	x.xx
AEs	Hepatobiliary disorders	n (%)	n (%)	n (%)	n (%)	n (%)	n (%)	xx.x (x.x to x.x)	x.xx
	Respiratory, thoracic and mediastinal disorders	n (%)	n (%)	n (%)	n (%)	n (%)	n (%)	xx.x (x.x to x.x)	x.xx
		n (%)	n (%)	n (%)	n (%)	n (%)	n (%)	xx.x (x.x to x.x)	X.XX
	Blood and lymphatic system disorders	n (%)	n (%)	n (%)	n (%)	n (%)	n (%)	xx.x (x.x to x.x)	x.xx
	Cardiac disorders	n (%)	n (%)	n (%)	n (%)	n (%)	n (%)	xx.x (x.x to x.x)	X.XX
	Gastrointestinal disorders	n (%)	n (%)	n (%)	n (%)	n (%)	n (%)	xx.x (x.x to x.x)	x.xx
ARs	Hepatobiliary disorders	n (%)	n (%)	n (%)	n (%)	n (%)	n (%)	xx.x (x.x to x.x)	X.XX
	Respiratory, thoracic and mediastinal disorders	n (%)	n (%)	n (%)	n (%)	n (%)	n (%)	xx.x (x.x to x.x)	x.xx
		n (%)	n (%)	n (%)	n (%)	n (%)	n (%)	xx.x (x.x to x.x)	x.xx
	Blood and lymphatic system disorders	n (%)	n (%)	n (%)	n (%)	n (%)	n (%)	xx.x (x.x to x.x)	x.xx
UARs	Cardiac disorders	n (%)	n (%)	n (%)	n (%)	n (%)	n (%)	xx.x (x.x to x.x)	X.XX
	Gastrointestinal disorders	n (%)	n (%)	n (%)	n (%)	n (%)	n (%)	xx.x (x.x to x.x)	x.xx

Doc No: ST06-RD01 Page **45** of **47**

		Nu	ımber of Eve	nts	Number of Patients				
		Total	Atropine sulfate	Placebo	Total N=	Atropine sulfate N=	Placebo N=	RR (95%CI)	p-value
	Hepatobiliary disorders	n (%)	n (%)	n (%)	n (%)	n (%)	n (%)	xx.x (x.x to x.x)	x.xx
	Respiratory, thoracic and mediastinal disorders	n (%)	n (%)	n (%)	n (%)	n (%)	n (%)	xx.x (x.x to x.x)	x.xx
		n (%)	n (%)	n (%)	n (%)	n (%)	n (%)	xx.x (x.x to x.x)	X.XX
	Blood and lymphatic system disorders	n (%)	n (%)	n (%)	n (%)	n (%)	n (%)	xx.x (x.x to x.x)	x.xx
	Cardiac disorders	n (%)	n (%)	n (%)	n (%)	n (%)	n (%)	xx.x (x.x to x.x)	X.XX
	Gastrointestinal disorders	n (%)	n (%)	n (%)	n (%)	n (%)	n (%)	xx.x (x.x to x.x)	x.xx
SAEs	Hepatobiliary disorders	n (%)	n (%)	n (%)	n (%)	n (%)	n (%)	xx.x (x.x to x.x)	x.xx
	Respiratory, thoracic and mediastinal disorders	n (%)	n (%)	n (%)	n (%)	n (%)	n (%)	xx.x (x.x to x.x)	x.xx
		n (%)	n (%)	n (%)	n (%)	n (%)	n (%)	xx.x (x.x to x.x)	X.XX
	Blood and lymphatic system disorders	n (%)	n (%)	n (%)	n (%)	n (%)	n (%)	xx.x (x.x to x.x)	x.xx
	Cardiac disorders	n (%)	n (%)	n (%)	n (%)	n (%)	n (%)	xx.x (x.x to x.x)	X.XX
SARs	Gastrointestinal disorders	n (%)	n (%)	n (%)	n (%)	n (%)	n (%)	xx.x (x.x to x.x)	x.xx
	Hepatobiliary disorders	n (%)	n (%)	n (%)	n (%)	n (%)	n (%)	xx.x (x.x to x.x)	x.xx
	Respiratory, thoracic and mediastinal disorders	n (%)	n (%)	n (%)	n (%)	n (%)	n (%)	xx.x (x.x to x.x)	x.xx
		n (%)	n (%)	n (%)	n (%)	n (%)	n (%)	xx.x (x.x to x.x)	x.xx

		Number of Events			Number of Patients					
		Total	Atropine sulfate	Placebo	Total N=	Atropine sulfate N=	Placebo N=	RR (95%CI)	p-value	
SUSARs	Blood and lymphatic system disorders	n (%)	n (%)	n (%)	n (%)	n (%)	n (%)	xx.x (x.x to x.x)	x.xx	
	Cardiac disorders	n (%)	n (%)	n (%)	n (%)	n (%)	n (%)	xx.x (x.x to x.x)	X.XX	
	Gastrointestinal disorders	n (%)	n (%)	n (%)	n (%)	n (%)	n (%)	xx.x (x.x to x.x)	x.xx	
	Hepatobiliary disorders	n (%)	n (%)	n (%)	n (%)	n (%)	n (%)	xx.x (x.x to x.x)	x.xx	
	Respiratory, thoracic and mediastinal disorders	n (%)	n (%)	n (%)	n (%)	n (%)	n (%)	xx.x (x.x to x.x)	x.xx	
		n (%)	n (%)	n (%)	n (%)	n (%)	n (%)	xx.x (x.x to x.x)	X.XX

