1.3 Study Objectives

The primary objective is:

 To evaluate the efficacy of 0.01% atropine eye drops to reduce the progression of myopia in children after 24 months of treatment.

The secondary objectives are:

- To evaluate the safety and tolerability of low dose atropine eye drops in terms of difficulties with near vision and reading, local discomfort and stinging of eye drops, photophobia, and occurrence of allergic reactions.
- To determine the mechanism of action of atropine eye drops. Specifically, we will evaluate if atropine has an effect on central axial length of the eye, position of the lens, peripheral retinal defocus and use of spectacle correction.

The exploratory objectives are:

• To explore the influence of other factors in the progression of myopia, including accommodation, chorio-retinal thickness at the macula, peripheral axial length, hours of outdoor activity, iris colour, ethnicity, and family history.

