2.2 Secondary outcome measures

- Central axial length: measured using a laser biometer at central fixation conditions
- Best corrected distance visual acuity (BCdVA) (uniocular and binocular): assessed using the logMAR ETDRS chart. This is a standard letter chart used in research to ensure accuracy and validity of the acuity measurements and has been shown to be repeatable in children
- Near visual acuity (VA) (uniocular and binocular): tested using near logMAR ETDRS at 40 cm
- Reading speed: measured with the Wilkins Rate of Reading test
- Pupil diameter: measured using an autorefractor
- Spectacle correction
- Tolerability: using a 4-point scale to quantify, from the point of view of the participant, (1) local irritation/stinging associated with eye drop instillation;
 - (2) photophobia; and
 - (3) difficulties reading and writing
- Adverse event rates and allergic reactions rates
- Quality of Life: measured using the EQ-5D-Y

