7.2 Secondary outcomes

For the secondary outcome analyses, results will be used from both eyes to investigate if atropine has an effect on the following endpoints at month 24; central axial length, pupil diameter, uniocular BCdVA and uniocular near VA. Each of these endpoints will be compared between the atropine and placebo groups using GEE and 95% CIs and will be adjusted for the corresponding baseline secondary outcomes (if available).

For the following endpoints at month 24; binocular BCdVA, binocular near VA, reading speed, and quality of life (i.e. EQ-5D-Y VAS and Index) comparisons between the atropine and placebo groups will be performed using analysis of covariance (ANCOVA) and 95% CIs and will be adjusted for the corresponding baseline secondary outcome (if available). Tolerability at month 24 will be compared between the atropine and placebo groups using an independent samples t-test. Spectacle correction at month 24 will be compared between the atropine and placebo groups using the chi-square test (or Fisher's exact test if appropriate). N(%) of spectacle correction (all day and sometimes) will also be presented by treatment arm.

The number of AEs, ARs, SAE, SARs, SUSARs and number (%) of patients experiencing these events will be reported. The chi-square test (or Fisher's exact test if appropriate) will be used to check whether incidences of adverse events differ between the treatment groups. Risk ratio and 95% CIs will be reported.

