- Tolerability stingy at month 24: mean (SD) by treatment arm, difference in means with 95% CI, p-value from independent t-test, in ITT and PP analysis.
- Tolerability itchiness at month 24: mean (SD) by treatment arm, difference in means with 95% CI, p-value from independent t-test, in ITT and PP analysis.
- Tolerability blurry vision at month 24: mean (SD) by treatment arm, difference in means with 95% CI, p-value from independent t-test, in ITT and PP analysis.
- Tolerability sore eyes at month 24: mean (SD) by treatment arm, difference in means with 95% CI, p-value from independent t-test, in ITT and PP analysis.
- Tolerability difficult to read/write at month 24: mean (SD) by treatment arm, difference in means with 95% CI, p-value from independent t-test, in ITT and PP analysis.

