8.10 Toxicity/ Symptoms

- AEs, no.events (%) by treatment arm, no. patients(%) by treatment arm, Risk ratio with 95% CI and p value
- ARs, no.events (%) by treatment arm, no. patients(%) by treatment arm, Risk ratio with 95% CI and p value
- SARs, no. events (%) by treatment arm, no. patients (%) by treatment arm, Risk ratio with 95% CI and p value
- UARs, no. events (%) by treatment arm, no. patients (%) by treatment arm, Risk ratio with 95% CI and p value
- SAEs, no. events (%) by treatment arm, no. patients (%) by treatment arm, Risk ratio with 95% CI and p value
- SUSARs, no. events (%) by treatment arm, no. patients (%) by treatment arm, Risk ratio with 95% CI and p value

Fatal AEs/SAEs, no. events (%) by treatment arm, no. patients (%) by treatment arm, Risk ratio with 95% CI and p value

AEs, ARs, SAEs, SARs, UARs and SUSARs will also be presented by system organ class.

Doc No: ST06-RD01 Page **21** of **47**

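### Coded adverse events stop at system organ class, so no table gives the rate of a specific reaction by arm, and allergic reactions and photophobia have no analysis

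*Supplement*

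**What the plan says.** Section 8.10 lists overall rows for AEs, ARs, UARs, SAEs, SARs, SUSARs and fatal events. The AR line is typical: "ARs, no.events (%) by treatment arm, no. patients(%) by treatment arm, Risk ratio with 95% CI and p value". It then adds one further level: "AEs, ARs, SAEs, SARs, UARs and SUSARs will also be presented by system organ class". Section 7.2 fixes the test (chi-square or Fisher's exact) and the measure: "Risk ratio and 95% CIs will be reported".

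The Appendix 1 shell, "Table XXX: Safety outcomes by system organ class and treatment group", follows this. Within each event category there is one row, one risk ratio and one p-value per class. There are five named classes and a blank row, and nothing below class level.

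The safety objective in 1.3 is specific. It names "difficulties with near vision and reading, local discomfort and stinging of eye drops, photophobia, and occurrence of allergic reactions". Section 2.2 lists "Adverse event rates and allergic reactions rates" among the secondary outcomes, and photophobia as one of three tolerability items.

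Symptoms are also analysed outside the event tables. Sections 8.5 and 8.8 compare six items between arms at months 6, 12, 18 and 24: eye feel, stinging, itchiness, blurry vision, sore eyes and difficulty reading or writing. The form is always a mean score, for example "Tolerability stingy at month 24: mean (SD) by treatment arm, difference in means with 95% CI". Pupil diameter, near VA and reading speed are compared as well.

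**The concern.** With an eye drop, many local reactions can be expected to fall into one class. A single risk ratio for that class cannot say which reaction is more common with atropine. In the all-AE block it also mixes drug reactions with whatever other eye events children have over two years.

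The symptom scores cover part of the safety objective, but they are mean scores at fixed visits, not the proportion of children who had a reaction over 24 months. They also leave two named harms uncovered. Allergic reactions have no row or analysis in 7.2, 8.5, 8.10 or Appendix 1. Photophobia is not among the six analysed item labels. If the eye-feel item is meant to carry it, the SAP does not say so.

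For these two harms, and for any eye event nobody anticipated, the class table is the only between-arm comparison below the overall totals. What is at stake is whether a named safety objective can be answered reaction by reaction. The primary efficacy result is not affected.

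**Working it through.** **Coverage of the harms named in 1.3 and 2.2**

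| Named harm | Compared by arm as | Event rate by arm |
|---|---|---|
| Near vision, reading | near VA, reading speed, read/write score, blurry vision score | none |
| Discomfort, stinging | stinging, sore eyes, itchiness, eye feel scores | none |
| Photophobia | nothing under that name | none |
| Allergic reactions | nothing | none |

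**Arm sizes.** The plan states no adverse event rate, so the only plan figures available are the arm sizes in sections 5 and 6.1, 193 and 96. They reproduce. A difference of 0.32 D, SD 0.7 D, 90% power, two-sided 5% (sidedness assumed) and 2:1 allocation give 76 and 152 independent observations. Multiplying by 1.9 and dividing by 2 eyes gives 72.2 and 144.4 children. Dividing by 0.75 (15% dropout plus 10% Chinese) gives 96.3 and 192.5.

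**Dilution.** All event rates here are assumptions. Let p be the risk of the specific reaction in an arm, and b the risk of any other eye event, equal in both arms and independent of the reaction.

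- Class risk = 1 − (1 − b)(1 − p).
- 95% CI for the risk ratio by the log method: SE = √[(1 − r₁)/(193 r₁) + (1 − r₀)/(96 r₀)], with r the class risk in each arm.
- Power by the normal approximation for two proportions, two-sided 5%.

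Example with p = 10% v 2% and b = 20%:

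- Atropine: 1 − 0.80 × 0.90 = 28.0%.
- Placebo: 1 − 0.80 × 0.98 = 21.6%.
- Risk ratio: 28.0/21.6 = 1.30.
- SE = √(0.72/54.04 + 0.784/20.736) = 0.226, so the CI is 0.83 to 2.02.

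| Background b | Class risk, atropine v placebo | Risk ratio (95% CI) | Power |
|---|---|---|---|
| reaction alone | 10.0% v 2.0% | 5.00 (1.16 to 21.6) | 73% |
| 5% | 14.5% v 6.9% | 2.10 (0.93 to 4.73) | 46% |
| 10% | 19.0% v 11.8% | 1.61 (0.87 to 2.99) | 33% |
| 20% | 28.0% v 21.6% | 1.30 (0.83 to 2.02) | 21% |
| 40% | 46.0% v 41.2% | 1.12 (0.84 to 1.48) | 12% |

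Simulation (4,000 trials per scenario, chi-square, or Fisher for small expected counts) gives 76% for the reaction alone and 21% to 22% at 20% background, in line with the formula.

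**Range.** For a three- to five-fold excess over a placebo risk of 1% to 4%, the class risk ratio is:

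- 1.32 to 2.73 at 5% background
- 1.17 to 2.06 at 10%
- 1.08 to 1.55 at 20%
- 1.05 to 1.34 at 30%

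**AR block.** ARs are by definition drug-related, so events judged unrelated drop out and b should be lower there. If 5% of children had a background event attributed to the drops, the example gives the 2.10 row. All related eye reactions still share that one ratio.

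**The case against.** The strongest reply is that the SAP already looks at specific symptoms. Six tolerability items are compared one by one at four visits, and pupil size, near acuity and reading speed are compared too. This stands. A reader might infer that harms are examined by organ class alone, and the SAP does not support that. The gap concerns event rates, and above all allergic reactions and photophobia.

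Second, the separate AR block removes events judged unrelated, so much of the dilution applies to the all-AE block. This also stands, although causality judgement is imperfect and the AR rows still pool all related reactions in a class.

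Third, the size rests on assumed rates. A reader might infer that the class risk ratio would sit near 1. That needs a background of roughly 20% to 30% or more, or a rare reaction; at 5% to 10% the ratio in the example is 1.6 to 2.1. Nor does any section say that a class interval spanning 1 would be read as no excess, and an interval reaching 2.02 would not support that reading.

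Fourth, the shell looks like a template with a blank row, so the absence of a named eye class is not itself an error. The SAP also does not say to which class eye infections or allergic reactions would be coded. Section 8 cites ICH E3 principles and 8.10 does not forbid a lower-level listing, but neither commits to one, while the shells are otherwise detailed.

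Finally, event-level rows would be imprecise. At 8% v 2% the event-level risk ratio is 4.0 (0.91 to 17.6) with 53% power, so its interval also spans 1. That limits how the rows are read, and is no reason to omit them.

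**Conclusion.** The point holds as a reporting gap. Coded events are planned as totals and by class, so the tables cannot show which reaction differs between arms, whatever the background rate. Two named harms, allergic reactions and photophobia, have no dedicated analysis.

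The masking is possible, not demonstrated. In the 10% v 2% example a five-fold excess appears as a class risk ratio between about 2.1 and 1.1 as background eye events rise from 5% to 40%, and power falls from 73% to between 46% and 12%. This assumes equal background in the arms, independence from the reaction, full recruitment at 193 v 96, and coding of all these events to one class. None of the event rates comes from the documents. This is a cheap improvement to the safety tables, not a threat to the trial's main conclusion.

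**What to change.** In 8.10 and the class shell:

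- Add event-term rows within each class for AEs and ARs: number and percentage of children by arm, and the between-arm estimate with 95% CI for the more frequent terms. One possible cut-off is 2% of either arm, which is 4 atropine or 2 placebo children (0.02 × 193 = 3.9; 0.02 × 96 = 1.9). The threshold is the trial team's choice. List rarer terms.
- Include explicit rows for allergic reactions and photophobia, and state which coded terms count towards each. If a tolerability item is meant to capture photophobia, say which.
- Keep the class rows as subtotals.
- State that event-term rows are descriptive.

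The cost is SAP wording, coding of event terms already collected and a longer table. No new data are needed. The downside is many sparse, imprecise rows, in which an isolated interval excluding 1 should not be over-read.
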